## 15 Statistical Considerations

The diagnostic performance of the Q-POC SARS-CoV-2 Assay (in terms of PPA and NPA) will be determined using the Roche Cobas 6800 SARS-CoV-2 Test, as an FDA-approved reference standard comparator assay. This will be done for the entire dataset and also for subsets classified by comparator Ct-banding ( $Ct \leq 25$ ,  $25 < Ct \leq 30$ ,  $Ct > 30$ ) for SARS-CoV-2. Diagnostic performance will be assessed as follows:

- Positive Percent Agreement (PPA) will be calculated as  $100\% \times (TP / (TP + FN))$ .
- Negative Percent Agreement (NPA) will be calculated as  $100\% \times (TN / (TN + FP))$ .
- PPA and NPA will include 95% CI.

Where:

- True Positive (TP) indicates that both the Q-POC SARS-CoV-2 Assay and comparator assay returned a positive result for the target.
- False Negative (FN) indicates that the Q-POC SARS-CoV-2 Assay returned a negative result for the target, while the comparator assay returned a positive result.
- True Negative (TN) indicates that both the Q-POC SARS-CoV-2 Assay and comparator assay returned a negative result for the target.
- False Positive (FP) indicates that the Q-POC SARS-CoV-2 Assay returned a positive result for the target, while the comparator assay returned a negative result.

The performance of the Q-POC SARS-CoV-2 Assay will be presented based on the overall study (all specimens of a claimed specimen type combined) as well as stratified by site and time since symptom onset.

QuantuMDx www.quantumdx.com	Review Period	Doc. ID	Version
Document Title: Q-POC SARS-CoV-2 Assay (Q27001) Clinical Performance Study Plan	1 year	QVTP-39	1.0

The rate of invalid/indeterminate results observed during the clinical study by site and overall will be reported. The prevalence of infection observed at each clinical site as determined by the comparator and the detection rate by the Q-POC SARS-CoV-2 Assay separately will be reported.

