### 13.1 Data Validity

Upon completion of each Q-POC run, the instrument should display the test status as 'VALID'. If any other test status is displayed, the run should be discarded.

The comparator RT-PCR assay, Roche cobas® SARS-CoV-2, uses two SARS-CoV-2 nucleocapsid targets. Target 1 is specific to the SARS-CoV-2 virus, but Target 2 is a pan-Sarbecovirus region of the nucleocapsid that is conserved and detects both SARS-CoV-1 and SARS-CoV-2. This comparator RT-PCR assay considers samples which are positive for Target 1 as positive for SARS-CoV-2 virus regardless of the status of Target 2 which can be invalid, negative, or positive

QuantuMDx www.quantumdx.com	Review Period	Doc. ID	Version
Document Title: Q-POC SARS-CoV-2 Assay (Q27001) Clinical Performance Study Plan	1 year	QVTP-39	1.0

and the sample is still SARS-CoV-2 positive if Target 1 is positive. If Target 2 is positive and Target 1 is either negative or invalid, then the result is a presumptive positive due to Target 2's promiscuity among Sarbecovirus members. The decision has been made to consider all presumptive positive results as invalid for this clinical performance study. Only the result of "SARS-CoV-2 RNA detected", according to the manufacturer's instructions for use, will be counted as positive in the clinical performance evaluation data analysis.

Any problems encountered during testing must also be communicated to the relevant facilitator(s) and to QuantuMDx.

Any invalid tests should be repeated at least once.

External Quality Controls will be run as per the Q-POC SARS-CoV-2 Assay product IFU and Roche cobas® SARS-CoV-2 IFU. External positive control runs must return positive results. External negative control runs must return negative results. If the incorrect result is returned, or the Q-POC™ instrument displays one of these test statuses as 'INVALID', the controls should be re-run. If repeats also fail, contact the facilitator(s) or QuantuMDx.

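### Does Section 15 need changing because NPA cannot be computed within comparator Ct bands and the banding Ct is not named?

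*Combined protocol and SAP*

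**What the plan says.** Section 15 (Statistical Considerations) opens with "The diagnostic performance of the Q-POC SARS-CoV-2 Assay (in terms of PPA and NPA) will be determined" against the Roche comparator. The next sentence reads "This will be done for the entire dataset and also for subsets classified by comparator Ct-banding". It lists three bands (Ct up to 25, above 25 to 30, above 30) and ends by specifying that the banding is for SARS-CoV-2. No sentence restricts the bands to PPA.

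The section then defines the measures. The text "Negative Percent Agreement (NPA) will be calculated as" is followed by 100% × TN/(TN + FP). A true negative means that "both the Q-POC SARS-CoV-2 Assay and comparator assay returned a negative result for the target". A false positive means that the Q-POC assay was positive "while the comparator assay returned a negative result". A 95% CI is to accompany both measures, with no interval method named.

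Section 13.1 (Data Validity) describes the comparator, which "uses two SARS-CoV-2 nucleocapsid targets". Target 1 is specific to SARS-CoV-2; Target 2 is a region shared across Sarbecoviruses. The comparator "considers samples which are positive for Target 1 as positive for SARS-CoV-2 virus regardless of the status of Target 2". Target 2 positive without Target 1 is a presumptive positive, which the study treats as invalid.

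Section 12.4 sets minimum targets of 50 comparator positives and 500 comparator negatives.

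**The concern.** Two things look wrong.

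First, a stratified NPA needs comparator negatives in each stratum. If the stratifying variable is the comparator's own Ct, negatives have no value on it. Half of the Ct-stratified estimates (three of six) could not be produced as written.

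Second, the comparator has two targets, so a specimen can have two Cts, one or none. If the bands used Target 2, or a mean of the two, a positive on Target 1 alone would fall in no band, and the band denominators would not add up to the overall PPA denominator. Where both Cts exist they could lie on opposite sides of 25 or 30.

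The band above 30 shows how the assay performs in weak positives, and it is likely to be small. A choice of Ct left open until the results are known could affect how that band looks.

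**Working it through.** There is no stated figure to reproduce here; the only stated N is 50 + 500 = 550, which is not in question.

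**Step 1. Which specimens have a Ct.** The nine combinations of target results, under the rules in Section 13.1:

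| Target 1 | Target 2 | Call in this study | Target 1 Ct | Target 2 Ct |
|---|---|---|---|---|
| positive | positive | positive | yes | yes |
| positive | negative | positive | yes | no |
| positive | invalid | positive | yes | no |
| negative | positive | presumptive, so invalid | no | yes |
| invalid | positive | presumptive, so invalid | no | yes |
| negative | negative | negative | no | no |
| negative | invalid | not stated | no | no |
| invalid | negative | not stated | no | no |
| invalid | invalid | not stated | no | no |

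The documents do not say outright that a negative has no Ct. It follows because any specimen with a signal on either target is called positive or set aside as invalid. The three states without a stated call have no Ct either, so they do not alter the result.

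**Step 2. NPA by band.** TN and FP both require a negative comparator. In each band TN + FP = 0, so NPA = 0/0 with no interval. If specimens without a Ct were put in the band above 30, that band would repeat the overall NPA and the other two would still be 0/0. Either way, no misleading number arises.

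**Step 3. Which Ct to band on.** All three positive states have a Target 1 Ct; only one of the three also has a Target 2 Ct. Banding on Target 1 puts each counted positive in exactly one band, and the denominators sum to all positives (50 at the planned minimum). Section 15 ties the bands to SARS-CoV-2, and Section 13.1 names Target 1 as the target specific to that virus. Nothing in the documents points to Target 2 or to a mean.

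**Step 4. How far a band's PPA could move.** The documents give no Ct distribution, so the band sizes are assumptions. An even split gives 50/3, or about 17 per band; a band of 10 illustrates a smaller one.

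From 8/10 = 80.0%, moving one specimen:

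- detected positive leaves: 7/9 = 77.8% (−2.2 points)
- detected positive enters: 9/11 = 81.8% (+1.8)
- missed positive leaves: 8/9 = 88.9% (+8.9)
- missed positive enters: 8/11 = 72.7% (−7.3)

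Two specimens can reach 10 points from 8/10, but only in some combinations that include a missed positive. Two missed positives leaving gives 8/8 = 100% (+20.0), whereas two detected positives leaving gives 6/8 = 75.0% (−5.0). From 16/17 = 94.1%, the largest change from two specimens is two missed positives entering: 16/19 = 84.2% (−9.9).

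For scale, Clopper-Pearson 95% intervals (an assumed method) are 71.3% to 99.9% for 16/17 and 44.4% to 97.5% for 8/10. These widths reflect the number of positives per band, and naming the Ct would not narrow them.

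**The case for a change.** The best case for a change is that the sentence cannot be carried out as written. Analysts would have to depart from a written plan, if only by leaving cells blank. The reference to SARS-CoV-2 does not fully settle the choice of Ct, because Section 13.1 describes both targets as SARS-CoV-2 nucleocapsid targets and Section 15 names neither. The band above 30 is where an assay is most likely to miss infections, and with two missed positives changing band an assumed 8/10 could become 8/8. One reworded sentence would close both gaps and would need no specimens or testing.

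The literal reading stands: NPA by band is planned and is empty. It also stands that the target is not named. What does not follow is any consequence for the study's results. An empty cell corrects itself. On the Ct, the alternative choices are hypothetical. How often a counted positive lacks Target 2, and how far the two Cts differ, are not given, so no size can be put on the effect. The 8/8 example needs both missed positives to switch band through the choice of target alone. The wide intervals concern small bands, which is a separate matter that rewording would leave as it is.

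**Conclusion.** No change to the plan follows. The NPA-by-band part is a wording slip: three cells with a zero denominator that any analyst will see and leave out, with no estimate altered. The unnamed Ct is a gap that analysts would fill sensibly with Target 1, the SARS-CoV-2-specific target and the only Ct that every counted positive has.

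The effect on the primary objective is nil. Overall PPA and NPA use all counted positives and negatives regardless of Ct, and the targets of 50 and 500 do not depend on the bands. The bands are a secondary description, and the available text attaches no hypothesis, acceptance criterion or sample size to them. Within an assumed band of 10, one specimen changing band moves PPA by at most 8.9 points; within a band of 17, two move it by at most 9.9 points. Both shifts are small beside the intervals for such bands.

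This rests on the inference that a comparator negative has no Ct, on reading the Section 15 bands as Target 1, and on illustrative band sizes that the documents do not supply.

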## 16 Deviations from the Clinical Performance Study Plan

The investigator is not allowed to deviate from the CPSP, except when a deviation is necessary to protect subject's rights, safety and well-being, or the scientific integrity of the clinical performance study.

Should a deviation from the clinical performance study plan be required, this will be communicated to QuantuMDx, QuantuMDx will record the deviation in a Deviation Record Template Form (QTEM-270) and circulated for approval with the relevant stakeholders. All deviations will be explained and referenced in the Clinical Performance Study Report. Should there be any major and/or repeated deviations, these will be recorded and corrective and preventative actions implemented via the Control of Non-Conforming Product Procedure (QQA-14).

## 17 Accountability of the IVD Medical Devices under Investigation

Access to IVD medical devices under investigation shall be controlled and these devices shall be used only in the clinical performance study according to this Clinical Performance Study Plan (QVTP-39).

The sponsor shall keep records to document the physical location of all IVD medical devices under investigation from shipment of the devices to the study site until return or disposal.

The principal investigator or an authorized designee shall keep records documenting the receipt, use, return and disposal of the IVD medical devices under investigation, which shall include, when applicable:

- a) The date of receipt
- b) The identification of each Q-POC instrument via serial number and Q-POC SARS-CoV-2 Assay Test cassettes via batch number
- c) The expiry date of the Q-POC SARS-CoV-2 Assay Test Cassettes
- d) The dates of use
- e) The date on which the devices under investigation were returned or disposed of
- f) The date of return of unused, expired or malfunctioning devices under investigation

QuantuMDx www.quantumdx.com	Review Period	Doc. ID	Version
Document Title: Q-POC SARS-CoV-2 Assay (Q27001) Clinical Performance Study Plan	1 year	QVTP-39	1.0

## 18 Statements of Conformity

The clinical performance study outlined in this plan (QVTP-39) shall be conducted in accordance with relevant local and national ethical principles.

The clinical performance study outlined in this plan (QVTP-39) should comply with the Federal Food, Drug, and Cosmetic Act (FD&C Act) and its implementing regulations and should ensure compliance with all other pertinent laws and regulations, including Occupational Health and Safety Administration (OSHA) regulations pertaining to biological hazards ("universal precautions").

The clinical performance study outlined in this plan (QVTP-33) shall not begin until the required approval/favourable opinion or waiver from the ethics committee and/or regulatory authority has been obtained, when applicable.

## 19 Informed Consent Process

Informed consent is documented by means of a written, signed and dated informed consent form. The default personal information collected on the consent form is Name and Date of Birth.

All individuals asked to consider taking part in research must be given information about the research, presented in terms and in a form that they can understand. The participant must sign and date this sheet to show they have read and understood it.

The Designated Individual (DI) or Person Designated (PD), in the DI's absence, will arrange for an informed consent session prior to the donation of any sample. For external volunteers, an online informed consent session or phone call will be held prior to the donation of any sample. Informed consent is recorded on the relevant form and once the DI/PD and the volunteer are happy that informed consent has been given, the sample will be obtained and labelled with the Sample ID assigned to the consent form.

A scanned copy of the signed informed consent form must be added to the secure HTA server and the original hard copy to be stored with the DI. It is the responsibility of the DI/PD to ensure this takes place. Once inputted into the database, only the person's Sample ID must be used in all lab books, data files etc. Personal information on the donor must not be referred to.

A new consent form MUST be completed for each new donation a participant consents to.

QuantuMDx www.quantumdx.com	Review Period	Doc. ID	Version
Document Title: Q-POC SARS-CoV-2 Assay (Q27001) Clinical Performance Study Plan	1 year	QVTP-39	1.0

## 20 Adverse Events, Adverse Device Effects and Device Deficiencies

All applicable adverse events shall be reported in an interim or final report of the clinical performance study and reported in compliance with the Federal Food, Drug, and Cosmetic Act (FD&C Act).
